Study Design and Treatment Allocation: This is a non-inferiority based, pragmatic, randomized controlled trial of antibiotics-first vs. appendectomy for the treatment of uncomplicated appendicitis with a concurrent observational cohort to characterize any selection bias associated with patients choosing to participate in the randomized trial, and to support the generalizability of study results. By necessity, this is an un-blinded study (patients will know if they were randomized to appendectomy or antibiotics), and analysts will know the treatment allocation of study participants. The DCC will generate and maintain randomization lists for each practice site. We will use block randomization within practice sites, with random blocks of 4, 6, or 8 subjects. Using block randomization ensures that equal numbers of subjects are randomized to the intervention and control arm and that the two groups are balanced at periodic enrollment intervals. We will also stratify randomization on presence appendicolith determined by imaging to ensure balanced across this important subgroup. Crossover, in the conventional manner, is defined treatmentassignments as a patient who is randomized to appendectomy who refuses to undergo surgery or someone who is randomized to antibiotics but chooses appendectomy before or after the antibiotics are started. Please see below for our specific definition of protocol compliance that will be used for a per-protocol analysis.

Outcome Measures: The primary outcome is the EQ-5Dat 4 weeks following randomization to treatment. Secondary patient reported outcome measures include the 10 PROMIS Global Health Short Form, the Decision Regret Scale, Gastrointestinal Quality of Life Index (GIQLI), healthcare utilization, days missed of work, days a caregiver missed of work, and work productivity. Clinical endpoints include: resolution of symptoms, rates of appendectomy, rates of appendicitis-related events (e.g., perforated appendicitis, additional course of antibiotics, more extensive surgical procedure, and drainage procedures), extent of operative and surgical complications, neoplasm and other pathology findings, adverse and serious adverse events, hospital days, clinic visits, and caregiver/patient "time in healthcare".

General Analytic Strategy: The primary evaluation of EQ-5Dat 4 weeks will be conducted using an intention-to-treat (ITT) analysis, where patient data areanalyzed according to the patient's randomized treatment assignment. Using this analytic approach in a non-inferiority study design comparing antibiotics-first treatment to appendectomy, we aim to test whether the global EQ-5D scores are not different by more than a margin of 5% (M = 5%). The margin (5%) was selected because it is within the meaningful clinical

important difference (MCID) threshold of the EQ-5D, which is 5-10%¹⁻³.

Primary Analysis. Aim 1: Patient-reported QoL, as measured by the EQ-5D at 4 weeks, will be assessed using a linear regression model that adjusts for an indicator of randomized treatment group assignment and for all factors used to stratify randomization (i.e., practice site and appendicolith). As recommended by the United States Food and Drug Administration guidelines on clinical trial design⁴, the estimated treatment effect and 97.5% one-sided confidence interval (CI) will be compared to the non-inferiority margin (M = -5%)⁵⁻⁷. We will conclude that antibiotics are non-inferior to appendectomy when the entire 97.5% one-sided confidence interval is greater than M, as in example scenario A (Figure 1). This is equivalent to a one-sided (alpha=0.025) test of the null hypothesis H₀: $\Delta \leq -5\%$, where Δ represents the difference in mean EQ-5D at 4-weeks comparing antibiotics-first to appendectomy-first. If the null hypothesis of H₀: $\Delta \leq -5\%$ is rejected at Figure 1. Example trial conclusions in a non-inferiority trial.

the final evaluation, we will then conduct a test of superiority to determine the level of statistical evidence supporting an alternative hypothesis $H_A: \Delta > 0\%$ (i.e., scenario B of Figure 1). For Sub Aim 1, we will similarly evaluate non-inferiority on patient-reported QoL among the cohort *with and without* appendicolith. Patients whose randomization was

performed for the incorrect appendicolith group (e.g., research coordinator selected the wrong button during randomization) will be assigned to the group representing their true status.

Aim 1 Secondary Analyses: Secondary analyses of the primary outcome measures will include examining the entire trajectory of EQ-5D QoL measurements for each patient using statistical methods for longitudinal data such as linear mixed effects models or generalized estimating equations (GEE).⁸

While crossovers are anticipated, the ITT approach is an appropriate primary analysis. We will conduct a secondary as-treated analysis of the primary outcome measure that appropriately accounts for patient- or provider-level characteristics found to be differentially represented among patients who crossover and patients in the antibiotics arm who are treated with appendectomy. Careful as-treated and secondary data analyses are of elevated importance towards understanding the effectiveness of the treatments and in assessing for whom antibiotics-first is an appropriate treatment.⁹ A simple as-treated analysis is problematic because randomization is broken when select patients in the antibiotics and do not undergo appendectomy. Thus, patients who are successfully treated with antibiotics and do not undergo appendectomy may differ demographically or clinically in ways that introduce bias in a naive as-treated analysis. Detry (JAMA 2014) recommends both an ITT and a careful per-protocol analysis to address treatment changes in non-inferiority trials where non-adherence, crossover, or treatment changes are present. If we find a difference between the ITT and as-treated results, the ITT results will be considered the primary analysis.¹⁰

Per-Protocol Analysis: It is important to consider subjects who do not follow the protocol since these individuals bias treatment group comparisons toward no difference, but this is the alternative hypothesis rather than the null hypothesis for non-inferiority trials. Therefore, it is recommended that an ITT analysis is augmented with a per-protocol analysis that considers only those subjects from both treatment groups who adhered to the protocol. Although such a subset analysis may have bias due to patient factors associated

with non-adherence to the protocol it is a valuable companion analysis that does not suffer from nonadherence bias in the way that ITT analysis may. Our protocol states the conditions that are considered to adhere to the protocol, therefore we use the following criteria:

- All patients: exclude not randomized in accordance to the protocol (i.e., meets all inclusion/exclusion criteria, randomization assignment followed)
- Surgical group: exclude subjects whose randomization assignment was ignored.
- Antibiotics group: exclude subjects whose randomization assignments were ignored, were not given protocol-described antibiotics, or who underwent an appendectomy (for non-protocol indications, as described by sites).

For the antibiotics group we have a direct measurement of whether eventual surgery is compliant with the protocol as reported by the sites. In the per-protocol analysis we will exclude subjects according to the criterion above, and then analyze EQ5D using mean differences and the associated confidence interval to judge non-inferiority similar to our ITT analysis plan.

As-Treated Analysis: We will consider a two-stage approach for this as-treated analysis: 1) To identify subgroups that are likely to require appendectomy and therefore should not be considered as good candidates for treatment with antibiotics-first, and 2) To estimate the complier average causal effect (CACE), which seeks to compare the outcomes of patients treated successfully in the antibiotics-first arm (i.e., did not ultimately have surgery) with patients randomized to the appendectomy arm who similarly would not have crossed over **had they been randomized to the antibiotics-first arm**. The CACE framework considers the ITT mean in each randomized arm as being comprised of two subgroup means: patients who would be successfully treated with antibiotics-first without appendectomy, and patients who would eventually require appendectomy after being treated with antibiotics-first. We are able to directly observe which patients in the antibiotics-first arm ultimately cross over, but require the CACE framework to identify similar patients in the appendectomy arm. We will use a maximum likelihood mixture modeling approach to identify the optimal comparison group from the control arm for observed compliers in the intervention arm.¹¹ This application of mixture modeling permits an examination of two aspects of intervention process, the prediction of early antibiotics failures in the appendectomy-first group and the examination the treatment effect on quality of life among patients who are suitable candidates for treatment with antibiotics first.¹²

Analysis of Secondary Patient-Reported Outcomes: We will also compare secondary patient reported outcomes (i.e., 10 PROMIS Global Health Short Form, GIQLI, and the Decision Regret Scale) using an ITT framework and linear regression models. Similar to the primary outcome measure, secondary patient-reported outcomes will be assessed using model-based point estimates and associated confidence intervals. The magnitude of effect will be judged a posteriori using margins that are of comparable magnitude as the EQ-5D in terms of the Cohen's d statistic. In an exploratory analysis, the complete longitudinal trajectory of all PRO metrics will be assessed with linear mixed effects models.

Exploratory Aim A Analysis Plan: Using only data from patients enrolled in the antibiotics-first arm, we will also examine the association of these characteristics with eventual appendectomy. The primary analysis will consider appendectomies performed for any reason. A secondary analysis will define appendectomies as those performed for: (1) acute clinical reason 0-30 days post randomization, (2) non-acute clinical reason and (3) recurrence after a period of symptom resolution (30+ days post randomization).

We will employ univariate logistic regression models to identify and characterize associations with unplanned appendectomy. If we find that a number of baseline characteristics are relevant and the rate of unplanned appendectomy is high enough (e.g., >10-15%), we will use multivariable analyses to compare these characteristics among those undergoing early appendectomy (defined within the first 30 days) and eventual appendectomy (4 weeks to 2 years). Due to the potentially large number of input variables, interactions, and longitudinal assessments we will also use modern model development methods such as the LASSO with boosting.^{13,14} Boosting provides a more sophisticated approach towards building multivariable

predictive models and allows nonlinear relationships between the input variables and risk of requiring appendectomy after first being treated with antibiotics. Boosting is a multiple prediction and aggregation method for classification, where a "base learner" fitting method is fitted multiple times on reweighted data and a final estimator is constructed through a linear combination of the multiple estimates. Results of these analyses will be considered hypothesis generating and may support secondary studies aimed at predictive modeling.

Aim 2 Analysis Plan: Clinical endpoints (see Outcome Measures above) will also be compared between ITT groups using regression models appropriate to each endpoint (e.g., linear, logistic, Poisson, or Cox proportional hazards regression models), along with a similar non-inferiority framework with margins based on MCIDs when available. **For Sub Aim 2**, we will similarly evaluate clinical endpoints among the cohort with and without appendicolith. The goal is to estimate treatment effects within each subgroup based on appendicolith.

Exploratory Aim B Analysis Plan: One assumption is that patients included in the randomized trial are sufficiently similar to those from the general population of patients with appendicitis. Using simple univariate descriptive and comparative statistics (e.g., t-tests, Chi-squared tests), we will compare randomized patients to those in the parallel observational cohort to identify selection bias. We will also compare the primary outcome measures between randomized and non-randomized patients by examining the entire trajectory of EQ-5D QoL measurements using linear mixed effects models or GEE for longitudinal data, providing an assessment of differences in the rate of change of quality of life. We will adjust for patient- or provider-level characteristics found to be differentially represented in RCT. Using methods similar to those described in the plan for Aim 1 Secondary Analyses, we will adjust for treatment received to fully assess whether patients who participate in the RCT have a different outcome trajectory than patients in the observational cohort.

Missing Data: We will conduct a missing data analysis to describe andcharacterize enrolled participants who do not provide data due to attrition. Specifically, we use 10-fold multiple imputation to assess the robustness of the results when missing data are imputed. In addition, as described by Molenberghs and Kenward (2007), we will also use inverse probability weighting in secondary analysis within each longitudinal regression model to inflate the weights of cases that are under-represented in the analysis due to selective attrition and/or non-participation. We will assess the sensitivity of inferences made from missing data first by using the two previously described methods for dealing with missing data and second, by imputing missing data under both pessimistic and optimistic scenarios to provide bounds on the statistical uncertainty. The characteristics of non-responders will be summarized in our final report and we will present the sensitivity of the estimated treatment effect due to alternative missing data methods.

Additional Exploratory Subgroups: We will also evaluate outcomes in selection subgroups including advanced age, sex, comorbid conditions and insurance status. For these analyses we will focus on evaluation of statistical interactions with treatment to assess treatment effect heterogeneity.

Statistical Analysis Plan References

1. Rabin R, de Charro F. EQ-5D: a measure of health status from the EuroQol Group. Ann Med. 2001 Jul;33(5):337-43. PMID:11491192

4. International Conference on Harmonisation E9 Expert Working Group. (1999). ICH harmonised tripartite guideline: statistical principles for clinical trials. Stat Med 18(15):1905-42. PMID:10532877

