4.4 Consent Process

The research coordinator and a representative from the medical team will confirm the patient's eligibility for the study based on inclusion and exclusion criteria. A research team member will approach all eligible patients and ask them to review an informed decision making video using a handheld device. The English or Spanish-language video explains both treatment options and the research study using linguistically and culturally appropriate language. In the event that the tablet is malfunctioning or the patient declines to watch the video, the research coordinator will provide an informational pamphlet that includes the same content as the video. There are two versions of the video and pamphlet, one focused on positive messaging, the other negative. Participants who present on odd calendar days will be shown Version 1; those who present on even days will be shown Version 2. Which version was shown to the patient will be documented on the screening form in order to determine whether phrasing outcomes in different ways impacts subject participation. The video and informational pamphlet both conclude with a

request of the patient to read and sign an informed consent document for participation in the randomization cohort.

- For patients consenting to randomization, they will be randomly assigned to either the antibiotics or appendectomy arm immediately following consent and assigned a study ID;
- b. Patients refusing consent to randomization may first be invited to participate in the observational cohort, and if that is declined, may then be offered participation in the EMR review cohort. This will be done by separate consent(s) with the participant selecting one of two participation options:
 - Option 1. Observational cohort (no randomization). Participants selecting the observational cohort will be asked to complete the same research assessment activities as the randomized cohort and will have their appendicitis treated following the same treatment protocols.
 - Option 2. EMR review cohort. Participants selecting this option will be followed by passive EMR review only. They will not be contacted again for study purposes and will not be asked to complete the Baseline Assessment or the Follow-Up Assessments described in Section 5.2.

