5.1 Study Schedule Overview

Consenting participants will be asked to complete research assessments on the topics and at the time points described in Table 2. Site research coordinators (RCs) will oversee the completion of the Baseline Assessment in-person and will also contact participants by phone to complete the Week 1 and Week 2 Assessments. Participants will then be contacted by phone, mail, or email by the UW study staff to complete the Week 4 Assessment, Quarterly Assessments for the first year, and Biannual Assessments in the second year after the participant's initial ED presentation.

Participants will be given the option to consent to extended follow-up beyond the two-year mark. These participants will be surveyed annually for another 3 years for a total follow-up period of 5 years.

Table 2. Participant Assessment Schedule.

			Follow-Up Time Point								Optional Extended Follow-up		
Item	Baseline First 4 Weeks		Month					Month					
		1	2	4	3	6	9	12	18	24	36	48	60
Patient Point of Contact	Site RC	_	ite C		UW	study	staff (Site RC	as backı	ıp)	UW	/ study s	staff
Contact Information	x	X	x	x	x	X	x	x	X	x	х	х	x
EQ-5D ²⁰	х			х	х	Х	х	x	x	x	х	х	х
10-PROMIS Global Health Short Form ²¹	х			х	х			х	х	х	х	х	х
PROMIS-Pain Intensity	x	X	x										
Symptom Onset	х												
Beyond Demographics*	х												
Treatment Satisfaction/Expectation	х			х	х								
Gastrointestinal Quality of Life (GIQLI) ²²				х	х			x	x	x	x	х	x
Healthcare Utilization		x	x	х	x	X	x	x	x	x	х	x	х
Signs & Symptoms of Appendicitis		х	х	х	х	х	х	х	х	х	х	х	х
Adverse Events		X	x	x	х	X	x	x	x	x	x	х	x
Decision Regret Scale ²³				х	х			x					
Major Life Changes				х	х	Х	х	х	Х	х	х	х	х
Work Productivity Index		х	х	х	х								
Return to Work Information		х	х	х	х								
Medication Use		X	x	x	x								
Treatment Strategy Change		х	х	х									

[name] Study Protocol Version 6.1 February 2019

*Includes the following topics: Demographics & Gender Identify, Caregiver Role, Instrumental Support, Employment/Student Status, Income, Pain Catastrophizing, Health Literacy, Social Support, Confidence in Treatment Success, Trust in Healthcare

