5.2 Research Assessments

5.2.1 Baseline Assessment (Index Encounter)

For all participants consenting to the randomized or observational cohorts, the research coordinator will support the participant as they complete the Baseline Assessment described in Table 2 (above). The Baseline Assessment should be completed in-person and *prior to revealing the participant's random treatment assignment; however, research coordinators are asked to document when the participant became aware of their assignment, should it be revealed prior to completion of the Baseline Assessment. Survey questions will be presented in the order of importance in the event that the participant is unable to complete the full battery of questionnaires. The research coordinator will also extract case report data from the medical record related to the index hospital visit.*

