8.3 General Analytic Strategy

The primary evaluation of EQ-5D at four-weeks will be conducted using an ITT analysis, where patients' data are analyzed according to the patients' randomized treatment assignment. Using this analytic approach in a non-inferiority study design comparing antibiotics treatment to appendectomy, we aim to test whether the global EQ-5D scores are not different by more than a margin of 5% (M = 5%). The margin (5%) was selected because it is within the meaningful clinical important difference (MCID) threshold of the EQ-5D, which is 5-10%.

1. Primary Analysis, Aim 1 - Patient-reported QoL, as measured by the EQ-5D at fourweeks, will be assessed using a linear regression model that adjusts for an indicator of randomized treatment group assignment and for all factors used to stratify randomization (e.g., practice site). As recommended by the United States Food and Drug Administration guidelines on clinical trial design. 26 the estimated treatment effect and 97.5% one-sided confidence interval (CI) will be compared to the non-inferiority margin (M = -5%). ²⁷⁻²⁹ We will conclude that antibiotics are non-inferior to appendectomy when the entire 97.5% one-sided confidence interval is greater than M (Figure 1, example trial conclusion A). This is equivalent to a one-sided (α=0.025) test of the null hypothesis H_0 : $\Delta < -5\%$, where Δ represents the difference in mean EQ-5D at four-weeks comparing the antibiotics treatment strategy to the appendectomy treatment strategy. If the null hypothesis of H_0 : $\Delta < -5\%$ is rejected at the final evaluation, we will conduct a test of superiority to determine the level of statistical evidence supporting an alternative hypothesis H_A : $\Delta > 0\%$ (Figure 1, example trial conclusion B). For Sub Aim 1, we will similarly evaluate non-inferiority on patient-reported QoL among the cohort without appendicolith.

[figure not shown]

Figure 1. Example Trial Conclusions in a Non-inferiority Trial.

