8.5 Sample Size and Statistical Power

Prior studies suggest that non-clinical outcomes (e.g., loss of time from work and pain scores) were similar between groups, but did not evaluate a global QoL measure. The EQ-5D QoL

index ranges from 0 (worst QoL) to 1 (highest QoL), where anchor-based methods have shown that the MCID ranges 5%-10%. Based on data from a prior study of appendectomy with EQ-5D scores at 12 weeks, we estimate that the mean EQ-5D for appendectomy patients will be 0.90 with a standard deviation of 0.12. In order to assess QoL differences between interventions, we will recruit a total of 1552 patients assuming a 90% follow-up at four-weeks. This gives the study high power (>99%) to rule out EQ-5D differences between-groups as small as 5% (e.g., if we observe treatment differences of 0 to 2%) and 80% power if we observe a treatment difference of 3% (Table 5, below).

Previous Washington State evaluations of patients undergoing appendectomy (Table 1). identified that 2-3% of the population is African American, 10-12% Hispanic, 10-15% are Medicaid beneficiaries, and 10% will be above 64 years of age. Recruiting 1552 total patients will allow for a subgroup evaluation based on older age and Medicaid beneficiary status. Assuming 50% recruitment of these populations we anticipate including ~500 Medicaid beneficiaries and ~450 patients ≥65 years. As demonstrated in Table 5, this study also has adequate power (>80%) to rule out differences of 5% for observed treatment effect of Δ =0% within subgroups as small as n=250 patients, or treatment differences of Δ =-1% within subgroups of at least n=400. For this reason, we expect the study will be able to assess these two subgroups. All other subgroup evaluations will be post hoc and used for hypothesis development only.

Table 5. Statistical Power to Declare Non-inferiority on Patient-reported QoL, Overall and by

Subgroup (Non-inferiority Margin, M = -5%, one-sided α =0.025).

Treatment Difference A	Overall		Subgroups	
Treatment Difference, Δ	N=1552	N=250	N=400	N=500
-3%	82.6%	-	-	-
-2%	99.4%	-	57.1%	67.9%
-1%	100%	62.4%	83.8%	91.4%
0%	100%	83.0%	96.4%	98.8%

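### The primary model could also adjust for the baseline EQ-5D that is already collected: an optional efficiency gain to a valid test, safe only with a rule for unusable baselines

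*SAP*

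**What the plan says.** The final SAP (Primary Analysis, Aim 1) fits a linear regression of Week 4 EQ-5D that "adjusts for an indicator of randomized treatment group assignment and for all factors used to stratify randomization (i.e., practice site and appendicolith". Protocol 8.3 has the same form: treatment arm, and then "for all factors used to stratify randomization (e.g., practice site". Neither text names baseline EQ-5D, and nor do the SAP's per-protocol and missing-data paragraphs. The SAP's secondary trajectory analysis could use it, but its role there is not described and that analysis does not decide non-inferiority.

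The measurement exists. In Protocol 5.1, "Table 2. Participant Assessment Schedule" marks EQ-5D at baseline. Protocol 5.2.1 asks that the Baseline Assessment be completed in person before the participant learns the assignment. If it is not, "research coordinators are asked to document when the participant became aware of their assignment". The same section allows for incomplete baselines, ordering the questions by importance "in the event that the participant is unable to complete the full battery of questionnaires".

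Two facts limit how baseline can be used. Under Protocol 4.4, consenting patients are "randomly assigned to either the antibiotics or appendectomy arm immediately following consent", so little time may pass before disclosure. The trial is also open, and the SAP states that "analysts will know the treatment allocation of study participants".

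**The concern.** The earlier value of the same scale is a natural covariate in a comparison of means. Leaving it out gives up whatever precision it carries and leaves chance baseline imbalance in the estimate. This matters most near a true 3% difference, where Protocol 8.5 plans 80% power and a modest change in interval width can decide whether the bound clears the margin.

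The remedy has its own risk. A value given after the patient knows the arm may already reflect reaction to the assignment. Whether a value was obtained before disclosure is itself settled after randomisation. A careless adjustment could therefore bias a test that is unbiased today.

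**Working it through.** **Inputs from the documents.** In Protocol 8.5, "we estimate that the mean EQ-5D for appendectomy patients will be 0.90 with a standard deviation of 0.12". Total N is 1552, with 90% followed at four weeks. The margin is 5% and one-sided alpha is 0.025 (Protocol 8.3, SAP). Power is stated as 80% at a 3% difference.

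**Assumed inputs.** r, the within-arm correlation of baseline with Week 4 EQ-5D, is taken as 0.1 to 0.5. f, the share of analysed patients with a usable pre-disclosure baseline, is taken as 1 or 0.8. The documents give neither.

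**Step 1: reproduce the plan.** Read the percentages as relative to 0.90, so the margin is 0.045 and the difference 0.027. Per arm, n = 2 × (0.12 × (1.96 + 0.8416) / (0.045 − 0.027))² = 697.7, so 698. Then 698 / 0.9 gives 776 per arm, or 1552 in total, which matches. Read as index points (0.05 and 0.03), the same N gives 87.6% power. Table 5 prints 82.6%, which neither reading gives.

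**Step 2: add baseline.** SE = 0.12 × √(4 × (1 − f r²) / (0.9 × 1552)), which is 0.00642 at r = 0. Power = Φ((margin − difference) / SE − 1.96). Example with r = 0.3 and f = 1: SE = 0.00642 × √0.91 = 0.00613, and Φ(0.018 / 0.00613 − 1.96) = 83.6%.

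| Assumed r | Power at 3%, relative scale, f = 1 | Same, f = 0.8 | Power at 3%, index points, f = 1 | CI narrowing, f = 1 | 95% range of shift from chance imbalance |
|---|---|---|---|---|---|
| 0 | 80.0% | 80.0% | 87.6% | 0 | 0 |
| 0.1 | 80.4% | 80.4% | 87.9% | 0.5% | ±0.0013 |
| 0.2 | 81.6% | 81.3% | 88.9% | 2.0% | – |
| 0.3 | 83.6% | 82.9% | 90.4% | 4.6% | ±0.0038 |
| 0.5 | 89.9% | 88.0% | 94.9% | 13.4% | ±0.0063 |

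Narrowing is 1 − √(1 − r²). The imbalance range is 1.96 × r × 0.00642. At a 2% difference, power on the relative scale is already 98.8% and reaches 99.8% at r = 0.5.

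**Step 3: check type I error of the planned test.** Simulation at the margin (1397 analysed, 6000 runs per case, usability unrelated to arm) gave 2.3% to 2.5% without baseline and 2.2% to 2.6% with it. Both agree with 2.5%.

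**Step 4: post-disclosure values.** If they are used and are shifted in one arm, the bias is about r × share × shift. With r = 0.3, shares of 10% to 30% and shifts of 0.05 to 0.10 (all assumed), it runs from 0.3 × 0.1 × 0.05 = 0.0015 to 0.3 × 0.3 × 0.10 = 0.009.

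**Step 5: unequal usability.** Assume r = 0.3, margin 0.045, and sicker patients more often unusable (log-odds 0.5 per SD of lower baseline). Bias is antibiotics minus appendectomy, so a positive value favours non-inferiority.

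| Unusable: appendectomy / antibiotics | Current model | Constant fill alone | Fill plus indicator |
|---|---|---|---|
| 30% / 10% | type I error 2.1% | bias +0.0027, type I error 5.9% | bias about −0.0006, type I error 1.8% |
| 10% / 30% | power at 3%: 79% | power at 3%: about 70% | bias about +0.0005, type I error 3.3% |
| 20% / 20% | power at 3%: 79.9% | power at 3%: about 82% | power at 3%: 82.6% |

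These are simulated values. A separate run of the first row gave 6.1% for fill alone against 2.4% for the current model. As an analytic check, type I error is about Φ(bias / SE − 1.96) with SE about 0.0062. A bias of +0.0027 gives Φ(−1.52) = 6.4%, −0.0006 gives Φ(−2.06) = 2.0%, and +0.0005 gives Φ(−1.88) = 3.0%. All are close to the simulated figures.

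The mechanism is simple. The fill value comes from healthier, usable patients. It makes the arm with more unusable baselines look better at baseline than it was, and the model then marks that arm down.

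**The case against.** The strongest reply is that nothing is broken. Adjusting for the stratification factors only is a legitimate pre-specified model, and the sample size reproduces without the covariate. That stands. A reader might infer that the primary test is invalid, or that the trial misses its stated power without baseline. The documents support neither.

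The second reply is that adjustment could do harm, because usability is determined after assignment in an open trial. This stands against filling with a constant alone, as Step 5 shows: the bias can run either way, including towards declaring non-inferiority. The indicator removes most of it but not all. With more unusable baselines in the antibiotics arm, simulated type I error was still 3.3%. That is why the current model needs to be the pre-specified fallback.

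The third reply is that the gain may be trivial. Baseline is taken during acute illness, so r may be low, and at r of 0.2 or below the gain is at most 1.6 points. This also stands. The 89.9% figure marks the top of an assumed range and is not an expectation.

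Finally, the final SAP is dated February 2020, interim analyses were planned at 400 and 800–1000 randomised, and the analysts know allocation. A late change to the deciding model needs a clear date and must precede any further comparison by arm.

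**Conclusion.** The point holds as an optional improvement. The deciding model omits a covariate that is already collected and whose pre-disclosure values should be identifiable from the records that Protocol 5.2.1 requires. The gain at a 3% difference is 0.4 to 3.6 points for assumed r of 0.1 to 0.3, and 9.9 points at r = 0.5. These are upper bounds on the scale that reproduces N = 1552, and they shrink as baselines become unusable. At 0 to 2% there is almost nothing to gain.

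Two further inferences should be resisted. One is that every recorded baseline can be entered; Protocol 5.2.1 itself foresees values completed after disclosure. The other is that the appendicolith, age or insurance subgroups would benefit; no gain is claimed for them. The results rest on r, the usable share and the usability mechanism, all of which are assumed. Severity: consider.

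**What to change.** Before any further comparison by arm, add a dated SAP paragraph that:

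- enters baseline EQ-5D as a linear covariate in the primary ITT model, using only values completed before the assignment was revealed;
- gives patients with a missing or post-disclosure baseline a constant set without regard to arm, together with an indicator for an unusable baseline, so that no randomised patient is dropped for want of a baseline;
- tabulates usability by arm before outcomes are compared, and states in advance what counts as a material difference;
- keeps the current model (arm, site, appendicolith) as primary if usability does differ materially, and otherwise reports it as a sensitivity analysis;
- uses the same model in any remaining conditional-power calculation under Protocol 8.6.

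Extending the term to Sub Aim 1 and the per-protocol analysis would be for consistency only.

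The cost is one paragraph, one table and one sensitivity analysis, with no new data collection. The downsides are a gain that may be under 2 points, a small residual bias (about 0.0005 in simulation) if usability is strongly unequal, and the need to show that the change was not chosen from results by arm. If these outweigh the gain, the current model can stand.
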